12.2.2 Follow up of adverse events

All adverse events will be followed clinically until they have been resolved, or until a stable situation has been reached. Depending on the event, follow up may require additional tests or medical procedures as indicated, and/or referral to the general physician or a medical specialist. Follow up information for grade 3 or 4 adverse events considered at least possibly related to the investigational medicinal product by the investigator should be reported on the AE CRF until recovery or until 6 months after the last dose of IMP, whichever comes first.

Follow up information for all other adverse events should be reported on the AE CRF until recovery or until 30 days after the last dose of any drug from the protocol treatment schedule, whichever comes first.

12.3 Serious Adverse Events

12.3.1 Reporting of serious adverse events

Serious Adverse Events (SAEs) will be reported from the first study-related procedure until 30 days following the last dose of any drug from the protocol treatment schedule or until the start of subsequent systemic therapy for the disease under study, if earlier.

Serious Adverse events occurring after 30 days should also be reported if considered at least possibly related to the investigational medicinal product by the investigator.

SAEs must be reported by **investigators** to the HOVON Data Center by fax **within 24 hours** after the event was known to the investigator, using the SAE report form provided. This initial report should contain a minimum amount of information regarding the event, associated treatment and patient identification, as described in the detail in the instructions for the SAE report form. Complete detailed information should be provided in a follow-up report within a further 2 business days, if necessary. When possible, signs and symptoms indicating a common underlying pathology should be noted as one comprehensive event.

Any clinically relevant deterioration in laboratory assessments or other clinical finding is considered an AE (also see 12.1 and 12.2.1)

The following events are not considered to be a Serious Adverse Event:

- Relapse/progression of the disease under study; complications as a result of disease progression remain reportable Serious Adverse Events
- Hospitalization for protocol therapy administration. Hospitalization or prolonged hospitalization for a complication of therapy administration will be reported as a Serious Adverse Event.
- Hospitalization for diagnostic investigations (e.g., scans, endoscopy, sampling for laboratory tests, bone marrow sampling) that are not related to an adverse event. Hospitalization or prolonged hospitalization for a complication of such procedures remains a reportable serious adverse event.
- Prolonged hospitalization for technical, practical, or social reasons, in absence of an adverse event.

Hospitalization for a procedure that was planned prior to study participation (i.e. prior to registration or randomization). This should be recorded in the source documents. Prolonged hospitalization for a complication of such procedures remains a reportable serious adverse event.

12.3.2 Causality assessment of Serious Adverse Events

The investigator will decide whether the serious adverse event is related to trial medication, i.e. any of the products from the protocol treatment schedule. The decision will be recorded on the serious adverse event report. The assessment of causality is made by the investigator using the following:

RELATIONSHIP	DESCRIPTION
UNRELATED	There is no evidence of any causal relationship
UNLIKELY	There is little evidence to suggest there is a causal relationship (e.g. the event did not occur within a reasonable time after administration of the trial medication). There is another reasonable explanation for the event (e.g. the patient's clinical condition, other concomitant treatments).
POSSIBLE	There is some evidence to suggest a causal relationship (e.g. because the event occurs within a reasonable time after administration of the trial medication). However, the influence of other factors may have contributed to the event (e.g. the patient's clinical condition, other concomitant treatments).
PROBABLE	There is evidence to suggest a causal relationship and the influence of other factors is unlikely.
DEFINITELY	There is clear evidence to suggest a causal relationship and other possible contributing factors can be ruled out.
NOT ASSESSABLE	There is insufficient or incomplete evidence to make a clinical judgment of the causal relationship.

12.3.3 Follow up of Serious Adverse Events

All serious adverse events will be followed clinically until they are resolved or until a stable situation has been reached. Depending on the event, follow up may require additional tests or medical procedures as indicated, and/or referral to the general physician or a medical specialist. Follow up information on SAE's should be reported monthly until recovery or until a stable situation has been reached. The final outcome of the SAE should be reported on a final SAE report.

12.3.4 Processing of serious adverse event reports

The HOVON Data Center will forward all SAE reports within 24 hours of receipt to the Principal Investigator, and the manufacturer of the investigational medicinal product Millennium The Takeda Oncology Company

The HDC safety desk will evaluate if the SAE qualifies as a suspected unexpected serious adverse reaction (SUSAR). The causality assessment made by the investigator will be used to determine reasonable causality. 'Unrelated' and 'unlikely' will qualify as 'no' and 'possible', 'probable', 'definitely' and 'not assessable' will qualify as 'yes'.

The IB will be used as a reference document for expectedness assessment.

The HOVON Data Center will ensure that a six-monthly line listing of all reported SAE's is provided to the Ethics Committee(s) if this is required by national laws or regulations or by the procedures of the Ethics Committee.

12.4 Reporting Suspected Unexpected Serious Adverse Reactions

The HDC Safety Desk, on behalf of the sponsor, will ensure the reporting of any SUSARs to the Ethics Committees (EC), the Competent Authorities (CA), Millennium The Takeda Oncology Company and the investigators in compliance with applicable laws and regulations, and in accordance with any trial specific agreements between the sponsor and co-sponsor or Millennium The Takeda Oncology Company t

Expedited reporting of SUSARs will occur no later than 15 days after the HOVON Data Center had first knowledge of the serious adverse event. For fatal or life-threatening cases this will be no later than 7 days for a preliminary report, with another 8 days for a complete report.

The manner of SUSAR reporting will be in compliance with the procedures of the Ethics Committees and Health Authorities involved.

12.5 Pregnancies

Pregnancies of a female subject or the female partner of a male subject, occurring while the subject is on protocol treatment or within 90 days following the last dose of any drug from the protocol treatment schedule, should be reported to the sponsor. Pregnancies must be reported to the HOVON Data Center by fax within 24 hours after the event was known to the investigator, using the pregnancy report form provided.

If the subject is on study drug, the study drug is to be discontinued immediately and the subject instructed to return any unused portion of the study drug to the Investigator. The pregnancy, suspected pregnancy, or positive pregnancy test must be reported to the Sponsor who will inform the manufacturer immediately. All details should be documented on the pregnancy form CRF. The patient

should be referred to an obstetrician/gynaecologist experienced in reproductive toxicity for further evaluation and counseling.

The investigator will follow the female subject until completion of the pregnancy, and must notify the sponsor of the outcome of the pregnancy within 5 days or as specified below. The investigator will provide this information as a follow-up to the initial pregnancy report. If the outcome of the pregnancy meets the criteria for classification as a SAE (i.e., spontaneous or therapeutic abortion, stillbirth, neonatal death, or congenital anomaly - including that in an aborted fetus), the investigator should follow the procedures for reporting SAEs. In the case of a live "normal" birth, the sponsor should be informed as soon as the information is available. All neonatal deaths that occur within 30 days of birth should be reported, without regard to causality, as SAEs. In addition, any infant death after 30 days that the investigator suspects is related to the in utero exposure to the investigational medicinal product(s) should also be reported.

The investigator is encouraged to provide outcome information of the pregnancy of the female partner of a male subject, if this information is available to the investigator and the female partner gives her permission. The HOVON Data Center will forward all pregnancy reports within 24 hours of receipt to the Principal Investigator and the manufacturer of the investigational medicinal product Millennium The Takeda Oncology Company.

12.6 Second Primary Malignancies

Second primary malignancies (SPM) will be monitored as events of interest and must be reported as serious adverse events. This includes any second primary malignancy, regardless of causal relationship to any study drug, occurring at any time for the duration of the study, from the time of signing informed consent until 8 years after registration in the trial or until completion of maintenance therapy for patients who are stil on maintenance at 8 years after registration.

Events of second primary malignancy are to be reported using the SAE report form and must be considered an "Important Medical Event" even if no other serious criteria apply. Documentation on the diagnosis of the second primary malignancy must be provided at the time of reporting as a serious adverse event (e.g. pathology report).

The incidence of second primary malignancies is also monitored via a separate form (Second Primary Malignancy Report Form). This form should be filled out, dated and signed by the responsible investigator and returned to the HOVON Data Center by fax within 14 days after establishment of a second primary malignancy.

SPM must also be documented in the other appropriate page(s) of the CRF (e.g. Adverse Event Form and Follow up Form).

For each case of SPM occurring during treatment, contact the Principal Investigator to discuss if treatment needs to be discontinued.

12.7 Reporting of safety issues

The sponsor will promptly notify all concerned investigators, the Ethics Committee(s) and the regulatory authorities of findings that could affect adversely the safety of patients, impact the conduct of the trial, increase the risk of participation or otherwise alter the EC's approval to continue the trial. In the occurrence of such an event the sponsor and the investigators will take appropriate urgent safety measures to protect the patients against any immediate hazard. The accredited Ethics Committee will suspend the study pending further review, except insofar as suspension would jeopardize the patient's health. The local investigator will inform the patients and local ethics or review committees according to hospital policy. The sponsor will inform any other parties that are involved in the trial.

12.8 Annual safety report

The sponsor will submit once a year a safety report to the Ethics Committees and Competent Authorities of the concerned Member States. The first report is sent one year after the first approval date of the trial. The last report is sent one year after the last patient has completed protocol treatment. The content of the annual safety report will be according to the EU guidance document 'Detailed guidance on the collection, verification and presentation of adverse reaction reports arising from clinical trials on medicinal products for human use'.

12.9 Data Safety and Monitoring Board

A data and safety monitoring board will be installed before start of the study.

The DSMB will advise the Principal Investigator, co-investigators and the chair of the working group in writing about the continuation of the trial. The DSMB will review the general progress and feasibility of the trial, the quality and completeness of the data, adverse events and safety. The DSMB will consider if there is any concern regarding the safety and well-being of trial subjects or regarding the scientific validity of the trial results. The DSMB will base its advice on the reports provided by the statistician. The DSMB is free to take into consideration external information, such as the (interim) results of other trials or literature reports.

The DSMB consists of at least three members, with at least one statistician and two physicians. Details of the DSMB constitution and tasks are documented in the trial specific DSMB charter.

The DSMB will receive at least the following reports from the trial statistician for review

- Interim analysis report (as described in 14.3)
- Annual safety data listing the incidence of (serious) adverse events, (serious) adverse reactions and SUSAR
- Annual progress data listing the number of enrolled patients and the status of data collection

12.10 Product Complaints

A product complaint is a verbal, written, or electronic expression that implies dissatisfaction regarding the identity, strength, purity, quality, or stability of a drug product. Individuals who identify a potential product complaint situation should immediately contact MedComm Solutions (see below) and report the event. Whenever possible, the associated product should be maintained in accordance with the label instructions pending further guidance from a Millennium Quality representative.

For Product Complaints,

call MedComm Solutions at [contact] ([name]) (US and International)

Please also inform the HOVON Data Center of your complaint by fax ([name]) or email (https://document.nl). Note that product complaints in and of themselves are not AEs. If a product complaint results in an SAE, an SAE form should be completed and sent to HOVON Data Center see section 12.3.1).

13 Endpoints

13.1 Primary endpoint

Maintenance treatment

 Progression free survival (PFS) from randomization, defined as time from randomization to progression or death from any cause, whichever comes first

Induction treatment

Response rate defined as sCR, CR, VGPR or PR

13.2 Secondary endpoints

- Safety and toxicity as defined by type, frequency and severity of adverse events as defined by the National Cancer Institute (NCI) Common Terminology Criteria for Adverse Events (CTCAE), version 4
- PFS from registration
- Overall survival (OS) from registration, measured until death from any cause. Patients alive
 will be censored at the date of last contact
- OS from randomization.
- Quality of response during maintenance, measured as improvement of response (from start maintenance till progression)
- Time to maximum response, defined as time from registration to maximum response
- Time to death from progression (after initial response), measured from time of first relapse/progression
- Time to next treatment
- PFS from the start of second line therapy
- Quality of life as defined by the EORTC QLQ-C30 and QLQ-MY20 definitions.
- Second Primary Malignancies

14 Statistical considerations

14.1 Patient numbers and power considerations

There are no data yet on PFS after 9 cycles of ixazomib citrate – thalidomide – dexamethasone induction chemotherapy. However, in the recently published MPR-R trial (Palumbo et al, NEJM. 2012; 366: 1759-69), median PFS for no-maintenance *after MPR* was 7 months. If ixazomib citrate - thalidomide – low dose dexamethasone is a more effective induction regimen, median PFS after randomization in the no-maintenance arm may be 10 months. Median PFS for lenalidomide maintenance *after MPR* was 26 months. An improvement of median PFS from 10 to 26 months with ixazomib citrate-maintenance equals a hazard ratio of 0.39. For the current sample size calculation the following assumptions have been used:

- uniform accrual for 18 months; additional follow up of 12 months after the last patient has been randomized;
- two-sided significance level a = 0.05;
- power $1 \beta = 0.90$;
- median PFS in the no-maintenance arm = 10 months:
- HR = 0.39.

This results in a total number of patients to be randomized of 94 (= 47 per arm), and the final analysis will be performed when 55 events after randomization have been reported (using the Freedman-Peto method). If we assume that 66% (based on the 34% discontinuation rate in the VISTA trial) of the patients will be randomized, then 94/0.66 = 142 patients have to be registered. However, in case the randomization rate is lower then expected, we will recalculate the number of patients that have to be registered, in order to achieve 94 randomized patients required for the primary endpoint. An estimate of the randomization rate will be performed in the first 50 patients.

Assuming a response rate of about 80% after induction chemotherapy, the 142 registered patients will enable to estimate the response rate with a standard error of about 3%.

14.2 Statistical analysis

All main analyses will be according the intention to treat principle i.e. patients will be analyzed according to the treatment arms they were assigned to. However, patients initially registered and/or randomized but considered ineligible afterwards based on information that should have been available before registration and/or randomization, whichever applicable, will be excluded from the respective analyses.

14.2.1 Efficacy analysis

The main endpoint will be PFS from the date of randomization. The formal test for difference in PFS between the two treatment arms will be done with a multivariate Cox regression analysis with adjustment for International Scoring System (ISS, I vs II and III), age (<75 vs ≥ 75 years) and response after induction treatment ((s)CR vs VGPR and PR). An estimate of the HR with corresponding 95% CI will be obtained. The actuarial Kaplan-Meier method will be used to estimate PFS probabilities at appropriate time points, while the Greenwood estimate will be used to construct corresponding 95% CIs. Competing risk analysis will be used to calculate cumulative incidences of PFS, progression/relapse, and death without progression (which add up to 100% at every time point). A Kaplan-Meier curve will be generated to illustrate PFS in each arm. In case the accrual will be 18 months, randomization will take place 9 months after registration of the last patient, and if 12 months of follow up after the last patient is required, then the final analysis may be performed after 18 + 9 + 12 = 39 months after start of the trial, if the complete and validated data including 55 events are available. The response rate after induction chemotherapy will be summarized as the proportion of patients with at least a PR, together with a 95% CI.

A preliminary efficacy analysis on response after induction treatment is planned when the data regarding induction treatment and response of the first 50 registered and eligible patients are available and have been evaluated. No conclusions will be drawn based on this analysis.

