5.1.2 Maintenance therapy

In general maintenance therapy with IMiDs or PIs have been found to increase response rates and PFS, however the impact on OS is less clear. Therefore, future clinical trials should aim to define the need, the optimum period and the type of maintenance therapy. There seems to be an improvement in outcome due to maintenance therapy with bortezomib with respect to PFS. However, this concerns a non head-to-head comparison of VMP with a once-weekly administration during 6 cycles followed by 3 years of maintenance therapy with either VP or VT with the historical data from the VISTA trial. Median PFS is longer (31 versus 24 months) indeed.⁵ Accordingly an increase in response was

observed during maintenance therapy. In addition, the Italian GIMEMA study showed that VT maintenance was feasible and resulted in an improved PFS and OS compared to no maintenance, however induction therapy was different in both arms; VMPT in the maintenance arm versus VMP in the non-maintenance arm. Therefore, the improvement in PFS and OS might not be solely due to maintenance therapy, although the difference in PFS and OS occurred during maintenance only. Moreover, it is currently unknown whether a treatment-free interval followed by re-treatment at relapse would at least equal the outcome compared to maintenance treatment until relapse. And the evolvement of therapy-resistant clones remains a concern. When taking thalidomide maintenance in account, subgroup analyses highly suggest a patient-tailored approach is necessary. This is exemplified by the fact that maintenance therapy with thalidomide was shown to result in an inferior outcome in patients with high risk cytogenetics. ^{10 11} This suggests the evolution of therapy-resistant clones indeed. Whether this holds true for proteasome inhibitor therapy is currently unknown. Especially long term treatment might induce therapy resistance. Therefore, correlative studies aiming at characterizing biological subgroups in more depth will be of critical importance in order to guide the duration and type of maintenance therapy.

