10.5 Central review

10.5.1 Cytogenetic review

FISH analysis is required in all patients at diagnosis/start of study. The following cytogenetic abnormalities will be evaluated as prognostic variables del1p, gain 1q, t(4;14)(p16;q32), t(14;16)(q32;q23), t(11;14)(q13;q32), del13q/13-, del17p and hyperdiploidy (at least 2 of the chromosomes 5, 9, 11 and 15 should be analyzed). Conditions for FISH will be according to the EMN guidelines (Ross et al., Haematologica 97, 1272-1277 (2012))

The cytogenetic review concerns a review of the original FISH data, cross checking original FISH data, data on CRF and data in the database

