14.2.4 Statistical analysis plan (SAP)

Before the final analysis, a SAP will be prepared by the trial statistician and approved by the principal investigator. It will describe in detail the analyses to be performed. Deviations from the analyses as specified in par. 14.2.1-14.2.3 will be discussed with the study coordinators and can only affect the exploratory analyses, but not the primary (confirmatory) analysis on which the sample size is based. All analyses except the primary analysis should be considered as hypothesis-generating only.

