The main objective of the study is to explore the prognostic value of focal lesions and SUVmax detected by FDG-PET-low dose CT at diagnosis with respect to progression free survival, as being described by two groups in a patient population undergoing autologous stem cell transplantation.^{7;8} A separate Cox regression model with PFS as outcome will be designed. In such a model, adjustments can be made for ISS, cytogenetic abnormalities [deletion 13, t(4;14), deletion 17p and amplification 1q], lactate dehydrogenase, biological bone markers, and GEP results. The hazard ratio's (HR) and associated significance levels from the different multivariate models will be compared with each other to obtain an indication which technique is most promising in terms of predicting the PFS. In order to assess the prognostic value of FDG-PET-low dose CT at diagnosis, various cut-off values for the FDG-avid focal-lesions and for SUVmax on PET may be employed. It is difficult to estimate the number of required patients to assess the prognostic value of a certain technique. Inclusion of 60 patients seems realistic, both in terms of participation rate and logistic restrictions. It is reasonable to assume that median PFS from registration in the HOVON-126 will be about 24 months. Furthermore, assume that half of the patients (n=30) have a "high" SUV of the lesion with the highest uptake, and expected 2-year PFS of 35% and half of the patients (n=30) have a "low" SUV of the lesion with the highest uptake and expected 2-year PFS of 65% (hazard ratio = 2.44). With uniform inclusion during 18 months (= expected accrual period of HOVON-126), additional follow up of 36 months after the last registered patient, and two-sided significance level $\alpha = 0.05$, we have 78% power to detect this difference. The analysis should be performed when in at least 43 patients in this side study an event for PFS has been reported (and 45 events for 80% power). Other cut-off points may result in different numbers of patients in subgroups, also with different PFS at 2 years and therefore other HRs. In fact, in the study of Bartel et al., more than 3 FDG-avid focal lesions was found in 34% of patients and to be significantly associated with a worse event-free survival; a HR of 2.98 was found. Similarly, in the study of Zamagni et al., more than 3 FDG-avid focal lesions, being observed in approximately 30% patients, was found to be significantly associated with a worse PFS; a HR of 1.80 was found. In addition, the 46% of patients with a SUV >4.2 were found to have a worse PFS; a HR of 2.19. However, it should be stressed that all these analyses are exploratory, so only hypothesis-generating, and results should be confirmed in other trials.

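### The primary Cox model is valid but leaves out cytogenetic risk, which FISH supplies at entry; adding it by amendment would be a cheap, modest gain in power

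*Protocol*

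**What the plan says.** - **Primary model.** Section 14.2.1 makes a multivariable Cox regression the formal test of PFS from randomization, with "adjustment for International Scoring System (ISS, I vs II and III), age (<75 vs ≥ 75 years) and response after induction treatment". Cytogenetics is not in it.
- **Locked.** Section 14.2.4 says departures in the later SAP "can only affect the exploratory analyses, but not the primary (confirmatory) analysis on which the sample size is based".
- **Allocation.** Section 15.2.2 minimizes on center and post-induction response. Cytogenetics is not a factor.
- **Data collected.** Section 10.5.1: "FISH analysis is required in all patients at diagnosis/start of study". It lists eight abnormalities whose prognostic value will be assessed. Appendix I makes sending marrow for FISH a condition of inclusion.
- **Rationale.** Section 5.1.2 reports that "maintenance therapy with thalidomide was shown to result in an inferior outcome in patients with high risk cytogenetics". It adds that it is not known whether the same applies to proteasome inhibitors.
- **Elsewhere in the analysis.** Section 14.2.3 places FISH among the exploratory prognostic factor analyses. The statistical section of the PET side study (Appendix J, section 13) says "adjustments can be made for ISS, cytogenetic abnormalities [deletion 13, t(4;14), deletion 17p and amplification 1q" among other variables, and calls all its analyses exploratory.

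**The concern.** Randomization protects the test whether or not a prognostic factor is in the model. In a Cox model, however, leaving out a prognostic baseline factor has a price even when the arms are balanced. The estimated treatment hazard ratio moves towards 1 relative to the ratio conditional on that factor, and power falls.

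The protocol already accepts adjustment for baseline factors that are not used in the minimization, since ISS and age are in the model. Cytogenetic risk is a further baseline factor that the trial pays to measure in every patient, yet it is used only in exploratory work. Because section 14.2.4 closes the primary model to the SAP, the omission cannot be put right there.

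**Working it through.** **Inputs from protocol section 14.1.** "two-sided significance level a = 0.05"; power 0.90; "An improvement of median PFS from 10 to 26 months with ixazomib citrate-maintenance equals a hazard ratio of 0.39" (10/26 is 0.385; the protocol plans on 0.39); control median 10 months; 18 months of accrual plus 12 of follow-up; 94 randomized 1:1; analysis at 55 events.

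**Step 1. Reproduce the planned size.** Freedman's formula gives

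d = (1.960 + 1.282)² × [(1 + 0.39)/(1 − 0.39)]² = 54.6, so 55 events.

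With exponential PFS the event probability per arm is 1 − (e^(−12λ) − e^(−30λ))/(18λ), with λ = ln 2/median. This is 0.751 for control (median 10) and 0.428 for active (median 10/0.39 = 25.6). The mean is 0.589, and 55/0.589 is about 93.3, so 94 patients. Both stated figures reproduce.

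**Step 2. Assumptions.** The protocol gives no prevalence and no hazard ratio for high-risk cytogenetics. Range used: prevalence 15-30%, hazard ratio 1.5-2.5, with 3 as an extreme.

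**Step 3. Simulate the design with and without the covariate** (true HR 0.39, control median 10 months, cut at the 55th event). Run (a) has treatment alone as the base model, 4,000 trials per row. Run (b) has three further binary covariates standing in for ISS, age and response (assumed hazard ratios 1.5, 1.2 and 0.6) in both models, 2,000 trials per row.

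| Run | Marker HR, prevalence | Estimated HR, omitted / included | Power %, omitted / included | Difference |
|---|---|---|---|---|
| a | 1.5, 15% | 0.392 / 0.385 | 91.8 / 92.0 | 0.2 |
| a | 1.5, 30% | 0.392 / 0.383 | 92.2 / 92.8 | 0.6 |
| a | 2, 15% | 0.399 / 0.385 | 91.3 / 92.3 | 1.0 |
| a | 2, 30% | 0.406 / 0.387 | 90.1 / 91.9 | 1.8 |
| a | 2.5, 15% | 0.405 / 0.384 | 90.3 / 92.2 | 1.9 |
| a | 2.5, 30% | 0.417 / 0.384 | 88.0 / 92.2 | 4.2 |
| a | 3, 30% (extreme) | 0.431 / 0.385 | 86.4 / 92.5 | 6.1 |
| b | 1.5, 25% | 0.392 / 0.381 | 91.8 / 91.8 | 0.0 |
| b | 2, 15% | 0.389 / 0.377 | 90.9 / 91.6 | 0.7 |
| b | 2, 30% | 0.406 / 0.385 | 89.2 / 91.4 | 2.2 |
| b | 2.5, 30% | 0.408 / 0.378 | 88.7 / 91.8 | 3.1 |

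The simulation error of one power figure near 90% is √(0.9 × 0.1/4000) = 0.5 points in run (a) and √(0.9 × 0.1/2000) = 0.7 in run (b). Both models are fitted to the same trials, so the differences are more precise than that.

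**Step 4. Smaller true effects, run (b).**

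| True HR | Marker HR, prevalence | Power %, omitted / included |
|---|---|---|
| 0.50 | 1.5, 25% | 71.5 / 71.4 |
| 0.50 | 2, 30% | 66.6 / 69.9 |
| 0.50 | 2.5, 30% | 64.6 / 69.8 |
| 0.60 | 1.5, 25% | 48.0 / 48.8 |
| 0.60 | 2, 30% | 44.4 / 47.0 |
| 0.60 | 2.5, 30% | 41.8 / 47.2 |

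**Step 5. No treatment effect.** Rejection rates with the marker omitted / included were 4.0-5.3% / 4.8-5.4% in run (a) and 5.2-5.6% / 5.5-6.1% in run (b). Median estimates stayed at about 1. The planned test keeps its level.

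**Step 6. Parameters.** The planned model has four: treatment, ISS, age and response, each binary. One FISH term makes five, 55/5 = 11 events each. An additional unknown level makes six, 55/6 = 9.2 each.

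**Limits.** The simulated marker is independent of the other covariates and known in everyone. Correlation with ISS or response, or failed FISH, would shrink the gain.

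**The case against.** The best defence is that nothing here is an error. The model is pre-specified, uses sensible covariates and holds its level, and its hazard ratio is valid given those covariates. Section 14.2.4 is ordinary protection against changes made after seeing data. FISH is already named for exploratory Cox work in 14.2.3, and a FISH-adjusted sensitivity analysis could go into the SAP without an amendment. All of this stands.

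Four stronger readings are tempting, and the documents do not support them:

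- **The protocol contradicts itself.** It does not. Section 10.5.1 plans to assess prognostic value and does not assert it. The side study only permits adjustment, in an exploratory setting, and its list also names LDH, bone markers and gene expression.
- **The primary estimate is biased or the test invalid.** It is attenuated only relative to a different, conditional hazard ratio. The model with the marker is not always nearer 0.39: at a marker hazard ratio of 1.5 and 30% prevalence it gave 0.383, against 0.392 without.
- **Chance imbalance corrupts the result.** With 47 per arm the SD of the prevalence difference is √(2 × 0.2 × 0.8/47) = 8 points at 20% prevalence, and just over 9 at 30%. That is ordinary sampling variation, which the test level and confidence interval already cover.
- **The thalidomide finding calls for this covariate.** It suggests that the treatment effect may differ by cytogenetic group, for another drug class. A main-effect term does not address that.

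**Conclusion.** The point holds as a missed efficiency gain. The confirmatory model does not use a baseline factor that the trial requires of every patient, and only an amendment can bring it in. At the design HR of 0.39 the cost is about 0-4 power points (about 6 in the extreme case), with the estimated HR moving from about 0.38 to 0.39-0.42. At true HRs of 0.50-0.60 the cost ranges from nothing to about 5 points. Type I error, the 55 events and the 94 patients are not in question. The sizes rest entirely on assumed prevalence and hazard ratio, so power stays close to the planned 90% unless the marker is both strong and common. This is a cheap improvement, not a correction the trial cannot do without.

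**What to change.** Amend section 14.2.1 before unblinding:

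1. Add one binary FISH covariate (high risk or not) to the primary Cox model.
2. Define high risk in the amendment, because the protocol does not. The definition can be built from abnormalities it already lists, for example t(4;14), deletion 17p and gain 1q, which appear in both 10.5.1 and Appendix J (there as amplification 1q), plus t(14;16) from 10.5.1.
3. State how failed FISH is handled: either extend the multiple imputation foreseen in 14.2.3 to the primary model, or use an unknown level.
4. Keep the present three-covariate model as a sensitivity analysis.

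The minimization, sample size and event count stay as they are. The cost is agreeing and freezing the risk definition in advance, and carrying five or six parameters on 55 events. The return is close to nothing if the marker proves weak or rare. If an amendment is not wanted, the reverse arrangement, with the FISH-adjusted model as a supporting analysis in the SAP, is open under 14.2.4 but does not recover power for the confirmatory test.
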